- Arm K (n = 84): initial treatment with an active regimen selected from Part 1, followed by ivermectin at Month 6;
- Arm L (n = 84): initial treatment with the same active regimen selected from Part 1 as Arm K, followed by ivermectin matching placebo at Month 6;
- Arm M (n = 84): initial treatment with a second active regimen selected from Part 1, followed by either ivermectin or ivermectin matching placebo at Month 6 (decision to be made prior to Part 2);

• Arm N2 (n = 84): 7 days of ABBV-4083 400 mg plus appropriate duration of albendazole matching placebo and ABBV-4083 matching placebo followed by either ivermectin or ivermectin matching placebo at Month 6 (decision to be made prior to Part 2).

In the Alternate Scenario, a minimum of 84 subjects with two or more operable sites will be enrolled to allow for approximately 21 subjects per arm to undergo a single-site nodulectomy at Month 6 for the evaluation of *Wolbachia* depletion but still have remaining onchocercomata for evaluation of skin microfilariae and other endpoints at Month 24. The overall design for Part 2 Alternative Scenario is presented in Figure 3.

Post-Study IVM rescue **IVM** Rescue Arm K Arm B. C or D IVM N = 84Arm L Same as Arm K IVM-Pbo N = 84Arm M Arm B. C or D IVM or IVM-Pbo N=84 4083-Pbo x 7d Arm N2 IVM or IVM-Pbo N=84 Alb-Pbo x 7d D6 D13 Screen D0 **M3** M6 M12 M18 M24 Skin snip Skin snip Skin snip Skin snip Skin snip Nodulectomy Nodulectomy (subset) Skin snip (1° endpoint) (Combination rule endpoint)

Figure 3. Overall Design for Part 2 - Alternative Scenario

4083 = ABBV-4083; Alb = albendazole; d = days; D = (study) day; IVM = ivermectin; M = month; Pbo = placebo

Rescue treatment with ivermectin will be offered at the investigator discretion to subjects with clinically significant worsening of symptoms and / or signs related to onchocerciasis at any time during the study or to subjects with increased mean number of microfilariae in the skin at Month 18, compared to the mean number at Month 12.

Post-study ivermectin will be provided after nodulectomy at 24 months to any subject with positive skin and/or eye microfilariae.

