If the primary hypothesis to satisfy the combination rule in Part 1 is not satisfied and ABBV-4083 + albendazole for 7 days (Arm C in Part 1) is to be carried forward to Part 2 (as either Arm K with ivermectin and Arm L without ivermectin, or as Arm M with or without ivermectin), an additional hypothesis using appropriate subjects from both Part 1 and Part 2 will be that more worms will have *Wolbachia* depletion at 6 months in subjects treated with ABBV-4083 + albendazole for 7 days (Arm C for Part 1 and Arm K plus Arm L [or alternately Arm M if appropriate] for Part 2) than in subjects treated with ABBV-4083 for 7 days (Arm A for Part 1 and Arm N2 for Part 2) among all subjects who completed treatment and who had live female worms from nodulectomies at 6 months.

In the case that ABBV-4083 for 7 days + albendazole for 3 days (Arm D in Part 1) is selected for Part 2 and ABBV-4083 + albendazole for 7 days (Arm C in Part 1) is not selected, and the primary hypotheses for satisfying the combination rule in Part 1 are not satisfied, then the arm or arms containing ABBV-4083 for 7 days + albendazole for 3 days will be treated as described elsewhere in this document for ABBV-4083 + albendazole for 7 days in the Alternate Scenario, and the data combined with Arm D in Part 1 for analysis.

10.1.3 Key Secondary Hypotheses in Part 2

The key secondary hypotheses in Part 2 are as follows:

- The first secondary hypotheses for Part 2 (Endpoint 2a) are that a smaller mean percentage of female adult worms per subject will be alive at 24 months among the subjects who completed treatment with one or more of three assigned regimens selected from Part 1 (Arms K, L and M) compared to either placebo (Arm N1) or ABBV-4083 for 7 days (Arm N2).
- The second secondary hypotheses for Part 2 (Endpoint 2b) are that a larger mean percentage of live female adult worms will have only degenerated embryos in their uteri

per subject at 24 months among the subjects who completed treatment with one or more of three regimens selected from Part 1 (Arms K, L and M) compared to either placebo (Arm N1) or ABBV-4083 for 7 days (Arm N2).

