For the Part 2 combination rule hypothesis in the Alternate Scenario that compares the proportion of live female adult worms without Wolbachia at Month 6 between the combination arms of ABBV-4083 + albendazole for 7 days (Arm K plus Arm L) and the ABBV-4083 single drug arm (Arm N2), 17 subjects per each of Arms K and L for a total of 34 subjects in Part 2 in addition to the 25 subjects per arm in Part 1 will be able to provide an overall power of 96% to detect the difference between the combination arm where 90% of worms are without Wolbachia and the single drug arm where 70% of worms are without Wolbachia (2-sided α =0.10) in either Part 1 or Part 2, using an inverse normal combination test that combines the pvalues of alternating logistic regressions that use data from Part 1 only and Part 2 only. The assumption for the number of worms in each subject in Part 2 is adjusted to a multinomial distribution with probability = (0.22, 0.18, 0.17, 0.16, 0.08, 0.06, 0.06, 0.03, 0.02, 0.02) for values (1, 2, 3, 4, 5, 6, 7, 8, 9, 10) in order to account for the design that only worms from one nodule per subject in Part 2 will be used for this analysis. If Part 1 Arm B of ABBV-4083 for 14 days is used for Arms K and L of Part 2, Arm M would be the 4083/albendazole combination that is compared to Arm N2. 17 subjects in Arm M Part 2 in addition to the 25 subjects per arm in Part 1 will be able to provide an overall power of 95% using the same method. Assuming 17% of the subjects per arm drop out by Month 6, the enrolment in the alternate scenario will require at least 25% of subjects of those retained to Month 6 nodulectomy to have > 1 nodule site in the arms used to test this hypothesis to obtain the power shown above.

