10.5 Population Level Summary and Analysis for the Primary Endpoints

The Part 1 primary and combination endpoints, the proportion of adult female worms without *Wolbachia* endobacteria assessed by immunohistology at 6 months, will be summarised among

the PP for ND6M population, and the odds ratio for each of the treatment arm comparisons of interest (Arm A vs E and Arm B vs E; Arm C vs E, Arm C vs A; Arm D vs E, Arm D vs A) will be calculated using contrasts within an alternating logistic regression model with treatment arm as factor and also accounting for within-subject correlation, each at 2-sided $\alpha = 0.10$.

The Part 2 primary endpoint of the percentage of subjects without skin microfilariae at Month 24 will be summarised across the PP for microfilariae population, and the adjusted odds ratio for each of the 3 active treatment arms will be compared to the comparator arm (Arm K vs N1 or N2, Arm L vs N1 or N2, and Arm M vs N1 or N2) using contrasts within a logistic regression model with treatment arm as factor and number of sites per subject (1, > 1) and mean baseline mf $(\le 5, > 5)$ as covariates at 2-sided $\alpha = 0.017$. Supportive subgroup analyses for the primary endpoint will also be performed for at least the following subgroups: number of sites per subject (1, > 1) and mean baseline mf $(\le 5, > 5)$.

The Part 2 combination rule endpoint for the alternate scenario, the proportion of adult female worms without *Wolbachia* endobacteria assessed by immunohistology at 6 months across all subjects treated with the same regimens in Parts 1 and 2 will be summarised among the PP for ND6M population, and the odds ratio for the comparison of interest (Arm K plus Arm L vs N2 [or Arm M vs Arm N2 if ABBV-4083 for 14 days is chosen for Arms K and L]) will be calculated using contrasts within an alternating logistic regression model with treatment arm as factor. P-values for the odds ratio of Part 1 and Part 2 will be combined using an inverse normal combination test and tested at 2-sided $\alpha = 0.10$.

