10.7 Multiplicity Adjustment

Since Part 1 is a Phase-II proof-of-concept study, no adjustment will be made for the multiple comparisons in the primary endpoint (Arm A vs Arm E, Arm B vs Arm E, Arm C vs Arm A, Arm C vs Arm E, Arm D vs Arm A and Arm D vs Arm E). Each comparison will be controlled at 2-sided $\alpha = 0.10$.

In Part 2, the multiplicity adjustment to control the overall Type I error rate at 5% will include: (1) Bonferroni allocation of $\alpha = 0.017$ to each primary endpoint comparison: Arm K vs Arm N1, Arm L vs Arm N1, and Arm M vs N1; (2) a graphical approach to multiplicity adjustment to control the family-wise error at 0.05 (see Figure 6). The same method will be used in the Part 2 Alternate Scenario, with comparisons between Arms K-M and Arm N2.

[figure not shown]

Figure 6. Graphical Approach to Multiplicity Control in Part 2

Of note, the parallel graphical approach above shows how the α is passed to the next comparison if the null hypothesis is rejected.⁸¹

In the Alternate Scenario of Part 2, the primary endpoint for satisfying the combination rule in Part 1 continued in Part 2 (combination rule endpoint) is conducted at 2-sided $\alpha = 0.10$ with no need to adjust for multiplicity per Section 5.5.2 of the European Medicines Agency Guideline on Multiplicity Issues for Clinical Trials.⁸²

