10.8 Statistical Analysis of Safety

All safety analyses will be performed on the Safety Population, which consists of all subjects who received at least one dose of IMP. Safety will be assessed by AEs, laboratory tests, vital signs, and ECG variables. Details of the analyses will be provided in the Statistical Analysis Plan.

AEs will be coded using the Medical Dictionary for Regulatory Activities (MedDRA). A TEAE is defined as an AE with an onset date that is after the first intake of IMP and no more than 30 days after the last intake of IMP. The number and percentage of subjects experiencing TEAEs will be tabulated using MedDRA system-organ class and preferred term, as well as by severity and by relationship to the IMP as assessed by the Investigator. Summaries of SAEs, deaths, AEs leading to discontinuation will also be provided.

For laboratory test and vital signs variables, mean change from baseline and percentage of subjects with on-treatment laboratory values of CTCAE 5.0 adapted scale grade 3 or 4 will be summarised.

10.9 Interim Analysis of Part 1 and DSMB Recommendation to Proceed to Part 2

Once subjects in Part 1 have completed or prematurely discontinued the study, up to and including nodulectomy at 6 months, a database lock for Part 1 database and an interim analysis of data from Part 1 will be conducted by the Sponsor and the randomisation code unblinded. The unblinded data will be reviewed by the Sponsor and the DSMB (see Section 13.3), for futility and risk/benefit ratio. Taking into account the recommendations of the DSMB, especially regarding the safety assessment of the data, the Sponsor will decide whether or not to proceed to Part 2, and with which dose regimens.

Selection of up to two acceptable/suitable doses / regimens for Part 2 will be based on analysis of all of available unblinded data from Part 1, including safety and tolerability of ABBV-4083 and ABBV-4083 + albendazole, *Wolbachia* depletion, disruption of embryogenesis and an exploratory surrogate marker, microfilaria *Wolbachia*, observed at Months 3 and 6.

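### The combination rule is tested twice, each time at the full 2-sided 0.10, so the chance of a false superiority claim is up to about 0.08 one-sided rather than 0.05, and the section 3.3 triggers for the second test overlap

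*Protocol*

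**What the plan says.** **First test.** Protocol 10.7 lists C vs A and D vs A among the Part 1 comparisons and makes no adjustment: "Each comparison will be controlled at 2-sided" 0.10.

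**Second test.** Protocol 10.1.2 adds a further hypothesis on Parts 1 and 2 together, conditional on the first test failing ("If the primary hypothesis to satisfy the combination rule in Part 1 is not satisfied") and on the combination going forward. Protocol 10.5 gives the method: "P-values for the odds ratio of Part 1 and Part 2 will be combined using an inverse normal combination test and tested at 2-sided" 0.10. Protocol 10.3.2 computes the 96% and 95% power for success "in either Part 1 or Part 2, using an inverse normal combination test that combines the pvalues" of the two parts.

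**Adjustment.** For the combined test, Protocol 10.7 sees "no need to adjust for multiplicity per Section 5.5.2 of the European Medicines Agency Guideline". No overall error for the pair of tests is given. Neither are the weights, nor whether one-sided or two-sided p-values enter the combination. The supplied SAP covers Part 1 only; its section 1.0 leaves Part 2 to a separate SAP.

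**Triggers.** Protocol 3.3 uses the Base Scenario if a combination arm is selected and C and/or D has beaten both A and E. It uses the Alternative Scenario if a combination arm is selected but C or D has not. Elsewhere Arm D is a substitute for Arm C: Protocol 10.1.1 and SAP 9.3.2 test D for the rule only if D advances and C does not, and Protocol 10.1.2 passes the retest to D only where "Arm C in Part 1) is not selected, and the primary hypotheses for satisfying the combination rule in Part 1 are not satisfied".

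**The concern.** An inverse normal test holds its level when it is the only test. It does not hold it when the first-stage data could already have won on their own. A combination that adds nothing has one chance to succeed by luck in Part 1 and, after a miss, a second chance in which the Part 1 result still counts. With the full level spent each time, the two-test rule has a larger error than the level the protocol quotes. The claim at stake is that albendazole contributes to the regimen.

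The overlap in 3.3 is a separate matter. The triggers decide whether the control is placebo (N1) or ABBV-4083 alone (N2), whether 294 or 336 subjects are enrolled, and whether Month 6 nodulectomies are done in Part 2. If both triggers are true, that choice would have to be settled after the Part 1 results are known.

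**Working it through.** **Inputs.** Level 2-sided 0.10 at each test, so one-sided 0.05 and critical value 1.645 in the favourable direction (10.5, 10.7). Part 1: 25 vs 25 subjects, 90% vs 70% of worms without *Wolbachia*, 81% power (10.3.1). Part 2: 34 in K+L, or 17 in Arm M (10.3.2). The evaluable size of N2 is not stated. I assume 17: 3.3 plans for "approximately 21 subjects per arm to undergo a single-site nodulectomy at Month 6", and 21 × 0.83 = 17.4 after the 17% dropout.

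**The plan's own figures.** A simulation with the stated ICCs and worm-count distributions, using cluster-robust log-odds as an approximation to alternating logistic regression, gave these powers:

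| | Simulated, independence weighting | Stated |
|---|---|---|
| Part 1 | 81.3% | 81% |
| Either test, K+L | 96.3% | 96% |
| Either test, Arm M | 95.2% | 95% |

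Exchangeable weighting gave 83.8%, 97.2% and 96.3%. The 96% does not by itself prove that two tests are intended, because the combined test alone gives 95.1% to 96.1% for K+L. The evidence for two tests is the wording of 10.1.2 and 10.3.2.

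**Weights (assumed from subject counts).** Let w be the squared first-stage weight. The information in each stage is n₁n₂/(n₁+n₂):
- Part 1: 25×25/50 = 12.5
- K+L vs N2: 34×17/51 = 11.33, so w = 12.5/23.83 = 0.524
- M vs N2: 17×17/34 = 8.5, so w = 12.5/21 = 0.595

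**Overall one-sided error.** Under the null, Z1 and Z2 are independent standard normals, positive in favour of the combination. If a combination that missed in Part 1 advances when Z1 > t:

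error = P(Z1 > 1.645) + P(t < Z1 ≤ 1.645 and √w·Z1 + √(1−w)·Z2 > 1.645)

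If it always advances, this is 0.050 + 0.029 = 0.079 (K+L) and 0.050 + 0.027 = 0.077 (M). The share of Part 1 misses that advance is (0.95 − Φ(t))/0.95; for t = 0.674 that is 0.20/0.95 = 21%.

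| After a Part 1 miss, advance if | Share of misses | K+L | M |
|---|---|---|---|
| always | 100% | 0.079 | 0.077 |
| Z1 > 0 | 47% | 0.078 | 0.076 |
| Z1 > 0.674 | 21% | 0.073 | 0.072 |
| Z1 > 1 | 11% | 0.067 | 0.067 |
| Z1 > 1.28 | 5% | 0.060 | 0.060 |

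With w from 0.7 to 0.3 and no selection, the range is 0.073 to 0.086.

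**Levels that restore 0.05 one-sided.** Solving the same formula for a total of 0.05 gives a 2-sided level at each test of 0.061 (K+L) or 0.063 (M). Alternatively, 2-sided 0.05 in Part 1 leaves 0.072 (K+L) or 0.075 (M) for the combined test.

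**Power at those levels.** A Part 1 drift of 2.523 gives the stated 81%. Part 2 drifts of 2.118 (K+L) and 1.961 (M) give the stated 96% and 95%.

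| | Part 1 power | Overall, K+L | Overall, M |
|---|---|---|---|
| 0.10 at both | 81% | 96% | 95% |
| equal split | 74% (K+L), 75% (M) | 93.5% | 92.3% |
| 0.05, then 0.072 or 0.075 | 71% | 94.1% | 93.0% |

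**Triggers in 3.3, read literally, with a combination arm selected:**

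| Part 1 result against both A and E | Base | Alternative |
|---|---|---|
| C and D both pass | true | false |
| exactly one passes | true | true |
| neither passes | false | true |

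Neither trigger is tied to the arm that was selected.

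**The case against.** Several points on the other side are sound.

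- **The plan is open about the structure.** It states 0.10 at both tests, counts success at either, and declines adjustment with a reason. A reader might infer that the two-test rule is concealed; the documents do not support that. Only the resulting error is missing. The cited guideline section is not available here, so I neither accept nor rebut the justification. It does not alter the arithmetic.
- **Weights and sidedness are normal content for the Part 2 SAP.** That is fair, and their absence from a Part 1 SAP is no fault. But in Protocol 10.9 the choice of "regimens for Part 2 will be based on analysis of all of available unblinded data from Part 1", and the sponsor sees those data. Weights or sidedness chosen after Z1 is known would undermine the method, so they must be fixed before then.
- **0.08 is a maximum.** A combination that adds nothing and has missed in Part 1 may not advance: Protocol 2.4.1 also weighs safety and the number and duration of drugs. The table shows 0.067 and 0.060 under strict selection. This lowers the figure but does not bring it to 0.05.
- **Doubling to about 0.16 two-sided would be wrong.** A reader might infer that error from the 2-sided levels. Half of it consists of rejections in which the combination is worse than ABBV-4083 alone, and those cannot satisfy a superiority rule.
- **Nothing says direction would be ignored.** The plan does not state how direction is kept when p-values are combined. That is a gap to close, not evidence of a directionless test.
- **The surrogate claim does not stand alone.** In the Alternative Scenario the selected regimens are also compared with N2 on skin microfilariae at Month 24, at 0.017 each. This limits the consequence but does not change the level of the combination rule.

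On the triggers, 10.1.1, 10.1.2 and SAP 9.3.2 do supply a hierarchy between C and D. Section 3.3, which chooses the scenario, does not carry it.

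**Conclusion.** The concern holds and should be fixed. As written, the combination rule does not have the level quoted for its tests: its one-sided error for superiority over ABBV-4083 alone is up to about 0.08, or 1.5 to 1.6 times the nominal 0.05. Every selection rule and weight examined leaves it above 0.05.

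The figures rest on three assumptions: weights from subject counts, 17 evaluable subjects in N2, and a combination that beats Arm E, which the rule also requires. They are normal-theory values for one combination arm, and leave out any small-sample excess in the model and any choice between C and D.

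The overlap in 3.3 is a real ambiguity with consequences for the control arm and sample size, but wording resolves it. The listing of D vs A without condition in Protocol 10.5 and 10.7, against the conditional test in 10.1.1 and SAP 9.3.2, is a wording difference only.

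**What to change.** **(a) Combination rule, before Part 1 is unblinded.** In Protocol 10.5 and 10.7, state the combination weights and that one-sided p-values are combined. Replace the implied level with the overall one-sided error for those weights (about 0.08 at most at the planned sizes). This costs wording only.

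Optionally, control the overall error at 0.05 one-sided with either split shown in the working: about 0.061 to 0.063 two-sided at each test, or 0.05 and then 0.072 to 0.075. Overall power falls from 96% to 93.5% or 94.1% (K+L), and from 95% to 92.3% or 93.0% (M). Part 1 would then miss at the planned effect 25% to 29% of the time instead of 19%, so the Alternative Scenario, with 336 − 294 = 42 more subjects and Month 6 nodulectomies, becomes somewhat more likely.

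**(b) Triggers, also before unblinding.** Reword 3.3 so that the triggers refer only to the selected combination arm or arms, are mutually exclusive, and agree with Protocol 10.1.1, 10.1.2 and SAP 9.3.2. If only one of C and D is selected, that arm's result decides. If both are selected, the sponsor states whether C decides or both must pass. If both must pass, either mixed result leads to 336 subjects; if C decides, only a C failure does.

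**(c) Wording.** Make Protocol 10.5 and 10.7 agree with 10.1.1 and SAP 9.3.2 on when D vs A tests the rule.

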10.6 Population Level Summary and Analysis for the Key Secondary Endpoints

The Part 2 secondary endpoint 2a, the mean percentage of live female adult worms per subject as assessed by histological examination of nodules collected during nodulectomy at 24 months, will be summarised among the PP for ND24M population and the mean difference between each of the 3 active treatment arms and the comparator arm (Arm K vs N1 or N2, Arm L vs N1 or N2, and Arm M vs N1 or N2) will be calculated using a stratified Mann-Whitney U test with number of sites per subject (1, > 1) and mean baseline mf $(\le 5, > 5)$ as strata, with α allotted according to the graphical approach in Figure 2. In the exploratory regimen/duration ranging, the percentage of live adult female worms per subject at Month 24 will be similarly compared between the 3 active arms, each at nominal 2-sided $\alpha = 0.05$.

The Part 2 secondary endpoint 2b, the mean percentage of live female adult worms with degenerated embryos in uterus per subject as assessed by histological examination of nodules collected during nodulectomy at 24 months will be summarised among the PP for ND24M with life female adult worms and the mean difference between each of the 3 active treatment arms compared to placebo (Arm K vs N1 or N2, Arm L vs N1 or N2, and Arm M vs N1 or N2) will be calculated using a stratified Mann-Whitney U test with number of sites per subject (1, > 1) and mean baseline mf $(\le 5, > 5)$ as strata, with α allotted according to the graphical approach in Figure 2. In the exploratory regimen/duration ranging, the mean percentage of adult female worms with degenerated embryos per subject and per nodule will be similarly compared between the 3 active arms, each at nominal 2-sided $\alpha = 0.05$.

The primary and key secondary endpoints will also be analysed on the ITT population.

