5.2 Secondary Efficacy Endpoints

5.2.1 Key Secondary Efficacy Endpoints in Part 2

The key secondary efficacy endpoints in Part 2 are:

- the proportion of live female adult worms per subject assessed by histological examination of all nodules collected after nodulectomy at Month 24;
- the proportion of live female adult worms with only degenerated embryos in uterus per subject as assessed by histological examination of nodules collected after nodulectomy at Month 24 out of all judgeable worms with embryos in uterus (normal or degenerated).

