10.3 Determination of Sample Size

10.3.1 Determination of Sample Size in Part 1

For the Part 1 primary hypothesis that compares the proportion of live female adult worms without *Wolbachia* at Month 6 between a single-drug ABBV-4083 arm (Arm A or Arm B) and the albendazole arm (Arm E), an alternating logistic regression will be used to compare the endpoint between two arms, taking into account the clustering of this worm-level endpoint by subject. Using simulations that add substantial clustering by subject to the endpoint values and assuming the number of worms in each subject varies from 1 to 10, ⁵⁴ following the multinomial distribution with probability = (0.20, 0.16, 0.16, 0.16, 0.08, 0.08, 0.08, 0.03, 0.03, 0.02) for values (1, 2, 3, 4, 5, 6, 7, 8, 9, 10), 17 subjects per arm will provide 88% power to detect the difference between a single-drug ABBV-4083 arm (Arm A or Arm B) where 70% of worms are without *Wolbachia* and the albendazole arm (Arm E) where 30% of worms are without *Wolbachia* (2-sided $\alpha = 0.10$). The clustering of the endpoint values by subject is provided by the Pearson intraclass correlation coefficient (ICC) for binary outcomes ⁸⁰ and was given as ICC = 0.54 for simulated arms where 70% or 30% of the worms are without *Wolbachia*.

For the Part 1 primary hypothesis that compares the proportion of live female adult worms without *Wolbachia* at Month 6 between the combination arm of ABBV-4083 + albendazole for 7 days (Arm C) and the single-drug ABBV-4083 arm (Arm A), 25 subjects per arm will provide 81% power to detect the difference between the combination arm where 90% of worms are without *Wolbachia* and the single-drug arm where 70% of worms are without *Wolbachia* (2-sided α =0.10 using alternating logistic regression). ICC = 0.54 was added to the simulated arm where 70% of the worms are without *Wolbachia*. Minimal clustering (ICC = 0.01) was added to the simulated arm where 90% of the worms are without *Wolbachia* because the difference between subjects would be negligible for such a high response rate. 30 subjects will be enrolled per arm to account for 17% drop out by Month 6.

10.3.2 Determination of Sample Size in Part 2

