The status of each nodule that contains at least 1 live adult female worm as without *Wolbachia*, as assessed by PCR at Month 6 will be summarized as the percentage of nodules without *Wolbachia* out of all nodules. The numerator and denominator of the percentage will be a sum across all subjects in a treatment arm. For the calculation of the percentages, nodules that do not contain live adult worms will be excluded from both the numerator and denominator. P-values for the pairwise comparison of each of Arms A, B, C, D with Arm E will be provided using the alternating logistic regression as detailed in Section 9.3.2 for the binary response per nodule clustered by subject.

The reduction in skin microfilarial density at Months 3 and 6 compared to baseline will be a mean change across all subjects summarized with descriptive statistics (number of subjects, mean and standard deviation, median, Q1, Q3, minimum, and maximum). The mean skin microfilarial density at baseline, Month 3 and 6 will also be summarized. Pvalues for the pairwise comparison of each of Arms A, B, C, D with Arm E will be provided using the Mann Whitney U test for the change from baseline in skin microfilarial

density per subject. The skin microfilarial density of each subject at a given time point will be collected as the final mean density of all the available skin snips. A supplementary analysis will be performed for this endpoint including only the final mean density values from  $\geq 2$  skin snips.

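### The exploratory per-nodule comparison of embryogenesis between the active arms in Part 2 uses a rank test with no allowance for several nodules from one subject, so its true level can exceed the nominal 5%

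*Protocol*

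**What the plan says.** Protocol 5.2.1 defines endpoint 2b at subject level: "the proportion of live female adult worms with only degenerated embryos in uterus per subject". Protocol 10.6 tests it against the comparator arm "using a stratified Mann-Whitney U test with number of sites per subject" and baseline microfilarial density as strata, under the graphical alpha scheme.

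The next sentence turns to the comparison among active regimens and labels it exploratory. There, "the mean percentage of adult female worms with degenerated embryos per subject and per nodule will be similarly compared between the 3 active arms", at nominal 2-sided 0.05 for each pair. The matching sentence for endpoint 2a is per subject only, so the nodule appears as a second unit of analysis for 2b alone. No method for nodules within a subject is named.

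In Part 1, the nodule-level PCR endpoint (SAP 9.4.2) goes through alternating logistic regression for the "binary response per nodule clustered by subject". Worm-level Wolbachia status is likewise modelled with within-subject association (Protocol 10.5, SAP 9.3.2). SAP 1.0 says that Part 2 will have its own SAP, which is not among the documents.

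**The concern.** Randomisation is by subject, and the stratification by one versus more than one operable site shows that some subjects are expected to contribute several nodules. The variance of a Mann-Whitney statistic assumes independent observations. Stratifying on the number of sites does not help, because the correlation lies among the nodules of each multi-nodule subject, inside the stratum. Applied per nodule, the test therefore counts too much information.

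Part 2 is meant to identify the regimen for Phase III, and these active-versus-active comparisons are its planned regimen-ranging evidence on worm sterilisation. A p-value that is too small could make two equivalent regimens look different. It could also disagree with the per-subject p-value for the same contrast, and nothing says which prevails.

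**Working it through.** **Inputs from the documents**

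- Evaluable subjects: 62 per active arm (Protocol 10.3.2, for the skin microfilaria endpoint).
- Within-subject ICC: 0.54 for arms at 30% or 70%, and 0.01 for the arm at 90% (Protocol 10.3.1). Both are worm-level values for Wolbachia at Month 6. None is given for embryo status, nodules or Month 24.
- Nodules per subject: not given. The nearest figure is a minimum of 25% of subjects with more than one site (Protocol 10.3.2, Alternate Scenario). Protocol 3.3 agrees: 84 of 336 = 25%.
- Worms from one nodule: the Part 2 distribution in Protocol 10.3.2, mean 3.53 (Month 6, Wolbachia analysis).

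**The plan's own figure.** The one stated figure for active against active is 80% power for 90% versus 70% with 62 per arm at 0.05. With a pooled null variance, z = (0.2·√62 − 1.96·√(2·0.8·0.2)) / √(0.9·0.1 + 0.7·0.3) = (1.575 − 1.109)/0.548 = 0.85, so power is 80.3%. It reproduces. The plan gives no error rate for the per-nodule test beyond the nominal 5%.

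**Approximate level.** With m nodules per subject, m′ = Σm²/Σm and design effect DE = 1 + (m′ − 1)·ICC. A test that ignores clustering has true level 2·[1 − Φ(1.96/√DE)].

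Example, 25% of subjects with two nodules and the rest with one: m′ = (0.75 + 0.25·4)/(0.75 + 0.5) = 1.4. At ICC 0.54, DE = 1.216 and the level is 7.6%.

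**Simulation.** Both arms had the same distribution, with 62 subjects each. Subject probabilities were beta-distributed with mean 0.7, each nodule held 1 to 3 worms (0.5/0.3/0.2, assumed), and the stratified Mann-Whitney test was run on nodule percentages.

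| Nodules per subject (assumed) | m′ | Formula, ICC 0.54 | Simulated, ICC 0.54 |
|---|---|---|---|
| All one | 1.0 | 5.0% | 4.7% |
| 25% two, rest one | 1.4 | 7.6% | 7.8% |
| 50% two, rest one | 1.67 | 9.3% | 10.0% |
| 1 to 4 (0.4/0.3/0.2/0.1), mean 2 | 2.5 | 14.5% | 15.6% |
| All three | 3.0 | 17.4% | 18.5% |

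The simulated values run slightly above the formula because 0.54 is a worm-level ICC. The percentage from k worms has ICC k·0.54/(1 + (k − 1)·0.54), which is 0.70 for two worms and 0.78 for three.

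**Sensitivity**

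- With the worm distribution of Protocol 10.3.2 in place of 1 to 3 worms, the second, third and fourth rows become 8.4%, 11.2% and 17.5%. Repeated runs of the mean-two case lie around 16 to 17%.
- At ICC 0.25, simulation gives about 7 to 13% over those nodule patterns. The formula gives 6.2% (DE = 1.10) to 9.5% (DE = 1.375).
- At ICC 0.01 the level is about 5%: even at m′ = 2.5, DE is only 1.015.
- The same test on one percentage per subject stays at 4 to 6% throughout.
- Sample size hardly matters. With 40 subjects per arm, mean two nodules and ICC 0.54, the level is 16% per nodule and 4% per subject.

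**The case against.** The case on the other side is substantial.

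- **The size is not in the documents.** A reader might infer that the test runs at about 16%, or that equivalent regimens will appear to differ two to four times as often as they should. That holds only for particular assumed nodule counts with ICC 0.54. The plan itself assumes almost no clustering at a 90% response, and Protocol 2.4.3 says that regimens advance only on strong Wolbachia depletion. Two good arms with little clustering are a relevant null, and there the inflation vanishes. This stands.
- **Few nodules may contribute.** Endpoint 2b needs judgeable live worms with embryos, so some nodules give no value. In the Alternate Scenario a subset loses one site at Month 6. The plan's mean worm counts, 3.79 per subject in Part 1 and 3.53 from one nodule in Part 2, also hint at few extra nodules. This favours the low end of the range but does not remove the problem.
- **This is not the only place without a clustering term.** A reader might infer an isolated lapse. The Wilson intervals on pooled worm percentages in SAP 9.3.2 and 9.6 have none either, so that contrast cannot be claimed.
- **The Part 2 SAP could name a clustered test.** It could, and the Part 1 nodule analysis is a precedent. As written, though, the protocol points to the Mann-Whitney test, which goes beyond missing detail.
- **The consequences are limited.** The comparison is exploratory, no decision rule uses it, and under Protocol 10.10 a Phase III recommendation may be made from safety and skin data at Month 18. This lowers the severity. But exploratory status waives multiplicity control; it does not make a p-value with the wrong variance valid.

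**Conclusion.** The concern holds in a limited form. The per-nodule comparison, followed as written, uses a test without a within-subject term. Its level exceeds 5% when subjects give more than one evaluable nodule and outcomes correlate within subject.

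The excess can be given only as a conditional range: negligible at ICC 0.01, and up to about 17% at ICC 0.54 with an assumed mean of two nodules. At the one documented multi-site share, read as two nodules each, it is about 8% even at ICC 0.54. The range rests on an ICC borrowed from another endpoint, level and visit, and on assumed nodule counts.

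The documents do not support any doubt about the alpha-controlled comparisons of 2b with the comparator arm, or about the per-subject comparison of active arms. Both use one value per subject. The label is wrong as written, low severity.

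**What to change.** In Protocol 10.6 and the Part 2 SAP, keep the per-subject stratified Mann-Whitney test as the only inferential comparison of 2b between active arms, and show per-nodule percentages descriptively.

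If a nodule-level test is wanted, specify one that respects the subject: a rank-sum test clustered by subject within the randomisation strata, or a permutation of arm labels by subject within those strata.

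The cost is one sentence, with no extra data or subjects. The downside is that nodule-level p-values become less favourable or are no longer reported.
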